3.2 Analysis Populations

3.2.1 Randomized Population

The Randomized population will include all patients who were randomized to the study.

3.2.2 Intent-to-Treat (ITT) Population

The ITT Population will include all patients who were randomized and received at least 1 dose of study drug.

3.2.3 Modified Intent-to-Treat (mITT) Population

The mITT Population will include all patients from the ITT Population who have valid baseline and Week 52 (or ET, if applicable) liver biopsy measurements; a valid Week 52/ET liver biopsy is

NorthSea Therapeutics B.V.	CONFIDENTIAL	Statistical Analysis Plan
Protocol NST-02		Version 1.0, 14 February 2023

defined as a liver biopsy that has occurred within 90 days of last dose/Week 52 visit. This will be the primary population for efficacy analysis.

3.2.4 Per-Protocol (PP) Population

The PP Population will include all patients from the mITT Population who complete the 52-week treatment period without any protocol violations that could impact on the primary efficacy endpoint. Patients who have a valid week 52/EOT biopsy within 30 days of last dose will be included in the PP population. The PP Population, along with the reason for exclusion, will be finalized prior to study unblinding.

3.2.5 Trough Pharmacokinetics (PK) Population

The Trough PK Population will include all patients who received at least 1 dose of NST-4016 and have at least 1 measurable trough PK concentration.

3.2.6 The Intensive Pharmacokinetics (PK) Population

The Intensive PK Population will include all patients who received at least 1 dose of NST-4016 and have at least 1 measurable non-trough intensive PK sample.

3.2.7 Safety Population

The Safety Population will include all patients who received at least 1 dose of study drug.

3.3 Patient Data and Study Conduct

3.3.1 Patient Disposition

Counts and percentages of patients who were screened (signed informed consent), screen failed, and randomized will be summarized overall based on all screened patients. Reasons for screen failure will also be summarized.

Counts and percentages of patients who were randomized, withdrew early from the study, including primary reason for withdrawal, and those that completed the study will be summarized by treatment group and overall based on the Randomized Population.

For each scheduled visit, counts and percentages of patients who do not complete the visit, partially complete the visit in-person, or complete the visit virtually will be summarized by treatment group and overall. The denominator for calculating percentages will be based on the ITT Population.

Data listings for patient disposition and exclusion and inclusion criteria violations will be provided.

3.3.2 Protocol Deviations

Protocol deviations will be identified based on the clinical data as defined in the Protocol Deviation Plan. The Protocol Deviation Plan will define all protocol deviations as either CSR reportable or non-CSR reportable. Counts and percentages of patients with CSR reportable protocol deviations by deviation category will be summarized by treatment group and overall, for the Randomized Population. A similar summary will be provided for Coronavirus Disease 2019 (COVID-19) related CSR reportable protocol deviations. A listing of CSR reportable deviations will also be generated.

3.3.3 Analysis Populations

Counts and percentages of patients in each analysis population will be summarized by treatment group and overall based on the Randomized Population. Reasons for exclusion from PP Population will also be summarized.

A listing of patients included in each of the study populations will be provided.

3.3.4 Demographic and Baseline Characteristics

Demographic and baseline characteristics will be summarized with descriptive statistics or counts and percentage of patients as appropriate by treatment group and overall, for the ITT population. If they differ from the ITT Population, summaries will also be provided for the mITT Population, the and the PP Population.

Demographic characteristics include age, gender, ethnicity and race.

Baseline characteristics include:

- Body Mass Index (BMI)
- Alcohol use (current/former/never)

Baseline histology includes:

- Biopsy fibrosis score (F1, F2 or F3)
- Biopsy fibrosis score for stratification (2 levels: F1 or F2/F3)
- NAS Score and individual scores for steatosis, ballooning, inflammation and fibrosis
- Composite Disease Activity Score composite NASH score of inflammation, ballooning and fibrosis.

Baseline chemistry includes:

- Liver enzymes (AST, ALT, ALP, GGT and bilirubin [Total, Direct and Indirect])
- Imaging parameters (MRI-PDFF and cT1)
- Biomarkers (HOMA-IR, hsCRP, Pro-C3 [COBAS] and ELF test)

All demographic, baseline characteristic, histology and chemistry data will be provided in by patient listings.

3.3.5 Medical History

Medical history will be coded to system organ class and preferred term using the Medical Dictionary for Regulatory Activities (MedDRA) version 22.0. Counts and percentages of patients with medical history by system organ class and preferred term will be summarized by treatment group and overall for the Randomized Population.

A listing of all medical history data will be provided.

3.3.6 Prior and Concomitant Medications

Prior and concomitant medications will be coded to World Health Organization (WHO) Drug Dictionary Global B3, March 2019. Prior medications include any medication taken within 6 months prior to screening. Concomitant medications include any medication taken on or after the date the patient signs informed consent.

Counts and percentages of patients taking prior and concomitant medications by Anatomical Therapeutic Chemical (ATC) class and preferred term will be summarized by treatment group and overall for the Safety Population.

All medications will be listed and flagged as either prior or concomitant (or both).

3.3.7 Study Drug Exposure and Compliance

Patients' exposure to study drug will be summarized with descriptive statistics for the Safety Population. Weeks of exposure to study drug will be calculated as:

(date of last dose of study drug – date of first dose of study drug + 1) / 7.

Note that the exposure duration calculation is intended to describe the length of time a patient was exposed to study drug and therefore does not take study drug interruptions into account.

Exposure to study drug will be summarized by treatment group for the Safety Population using descriptive statistics. Furthermore, exposure will be summarized in the following categories:

- ≤4 weeks (≤28 days)
- >4 to ≤10 weeks (29 70 days)
- >10 to ≤16 weeks (71 112 days)
- >16 to \leq 24 weeks (113 168 days)
- >24 to \leq 32 weeks (169 224 days)
- >32 to ≤ 40 weeks (225 -280 days)
- >40 to ≤ 52 weeks (281 364 days)
- > 52 weeks

Summary statistics will be presented for overall compliance to study drug by treatment group. Percent compliance will be calculated as:

 $\frac{number \ of \ actual \ capsules \ taken}{number \ of \ expected \ capsules \ taken} \times 100$

The number of actual capsules taken will be calculated as number of capsules dispensed – number of capsules returned. If study drug is not returned, the number of capsules returned will be considered 0 for the compliance calculation. The number of expected capsules will be derived from the dates of randomization and the earliest of the Visit 9 (Week 52) and ET dates, assuming 2 capsules are taken each day. Descriptive statistics will be used to summarize the compliance to the study drug by treatment group for the Safety Population. Additionally, the number and

percentages of patients in each treatment group will be provided with compliance in the following categories:

- <75%
- 75-125%
- >125%

Listings of drug accountability and derived exposure and compliance will be provided for the Safety Analysis Set.

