## 5.5.2 Study Drug Preparation and Dispensing

Study drug will be dispensed as 300 mg capsules for oral administration at Visits 2 to 8 by blinded site personnel. Patients will receive enough study drug to last until the next study visit.

This study protocol includes contingency measures to manage disruptions due to COVID-19 control measures, including modifications to study drug dispensation specific to situations where COVID-19 is impacting study conduct. See Appendix G for details of COVID-19 contingency measures. In the absence of a COVID-19 impact, it is expected that Investigators and patients follow the protocol requirements as set forth.

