## 5.5.3 Study Drug Administration

All patients will take 2 capsules of study drug (either 300 mg NST-4016 and/or matching placebo) orally in the morning with water once daily for 52 weeks. In the event that the Visit 9 biopsy is delayed, patients will continue to administer study drug daily until the biopsy occurs, for up to 30 days after the originally projected Visit 9 date.

Patients should take study drug at approximately the same time each day. Study drug can be taken in the fed or fasted state.

On study visit days, patients should take their daily dose of study drug at the clinical site to accommodate predose trough PK sampling.

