# 5.5.4 Treatment Compliance

The quantity of study drug dispensed to and returned by the patient will be counted by site personnel and verified by the Clinical Research Associate (CRA) monitoring the study. All discrepancies in drug accountability should be explained and documented (missed dose, lost capsule, overdose, etc). If the patient is not compliant with study drug intake, the Investigator should discuss this with the patient.

If study drug compliance drops below 80% or surpasses 100% at any given time during the treatment period, the Investigator or designee should discuss compliance with the patient and counsel the patient appropriately. Noncompliance includes missed doses in addition to taking the

wrong dose. The Investigator must continually encourage compliance with the study drug and with the study procedures.

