3.4.2.3 Liver Enzymes

Liver enzymes are assessed at Screening, Visit 2 (Week 0), Visit 3 (Week 4), Visit 4 (Week 10), Visit 5 (Week 16), Visit 6 (Week 24), Visit 7 (Week 32), Visit 8 (Week 40), Visit 9 (Week 52), Visit 10 (Week 54) and at the ET Visit.

The change and percent change from baseline in AST, ALT, ALP, GGT and total bilirubin at each scheduled visit will be analyzed using a Mixed Model Repeated Measures (MMRM) model, with change (or percent change) from baseline as the dependent variable, adjusting for treatment (300 mg NST-4016, 600 mg NST-4016, or placebo), visit, treatment-by-visit interaction, biopsy fibrosis score (2 levels: F1 or F2/F3); and baseline score. The Restricted Maximum Likelihood (REML) estimation approach will be used with an unstructured covariance matrix. The LS means, standard errors, 95% confidence intervals, and p-values for the pairwise treatment comparisons between each NST-4016 dose and placebo will be estimated for each visit.

At visits where the fasted status of the patient is recorded (Visit 2 (Week 0), Visit 5 (Week 16) and Visit 9 (Week 52)), only samples taken in a fasted state will be included. All results from other visits will be included. An additional analysis will be carried out to include patients who we fasted at all three visits where fasted status is recorded.

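### SAP 3.3.7 scores unreturned capsules as taken, so compliance can only err upward for patients who do not return drug, most of all early stoppers who attend ET

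*SAP*

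**What the plan says.** SAP 3.3.7 defines percent compliance as actual over expected capsules, times 100.

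- **Numerator:** "The number of actual capsules taken will be calculated as number of capsules dispensed – number of capsules returned". For missing drug: "If study drug is not returned, the number of capsules returned will be considered 0 for the compliance calculation".
- **Denominator:** it runs from randomization to "the earliest of the Visit 9 (Week 52) and ET dates, assuming 2 capsules are taken each day". The SAP gives no rule for a patient who has neither date.
- **Use:** descriptive statistics and three bands (below 75%, 75 to 125%, above 125%) by treatment group in the Safety Population, plus patient listings.

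The protocol adds the following:

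- **Dispensing (5.5.2):** "Patients will receive enough study drug to last until the next study visit". Appendix G allows extra supply under the COVID-19 measures.
- **ET visit (6.5):** it is requested promptly after the last intake, with no maximum gap.
- **Delayed Visit 9 biopsy (5.5.3):** dosing goes on until the biopsy, "for up to 30 days after the originally projected Visit 9 date".
- **Accountability (5.5.4):** sites count capsules, the monitor verifies the count, and discrepancies, including lost capsules, are explained and documented.
- **Overdose (8.6):** where accountability does not balance, overdose is established only if extra intake is clear or the investigator has reason to suspect it.

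**The concern.** A bottle that was lost, discarded or kept at home is treated as a bottle that was consumed. The true intake from it is unknown, and the rule replaces the unknown with its maximum. For a patient who finishes the study, this can turn a long gap in dosing into full compliance. For a patient who stops early, it credits capsules meant for days after the denominator has ended, and the result can look like overdosing that never happened. Neither outcome fits Protocol 5.5.4, which has the reason for a discrepancy recorded, or Protocol 8.6, which does not presume overdose from a count.

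What is at stake is a by-arm table that readers consult when a result is null or appears dose-related. Early stopping could differ by arm: Protocol 1.4.1.3 reports interim nausea of 4.3%, 9.0% and 21.3% on placebo, 300 mg and 600 mg. Unequal non-return is therefore possible, but the documents do not show it.

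**Working it through.** The documents state no compliance figure, so there is none to reproduce. I applied the SAP formula to the protocol schedule.

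**Inputs.** Visit days from Protocol Appendix A: 0, 28, 70, 112, 168, 224, 280, 364. At 2 capsules a day with supply to the next visit and no overage (assumption), Visits 2 to 8 dispense 56, 84, 84, 112, 112, 112 and 168 capsules, 728 in total.

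**Formula.** Reading = 100 × (dispensed − returned) / (2 × days from randomization to the earlier of Visit 9 and ET). I use elapsed days. The SAP does not say whether one day is added; adding it changes 140/70 to 140/72 = 194%, which is immaterial here.

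**1. Last dispensation not returned, ET attended**

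| ET day | Dispensed | Expected | SAP reading | Actual if dosing stopped at the last dispensing visit | Actual if dosed to ET |
|---|---|---|---|---|---|
| 35 | 56 + 84 = 140 | 70 | 200% | 56/70 = 80% | 70/70 = 100% |
| 126 | 56 + 84 + 84 + 112 = 336 | 252 | 133% | 224/252 = 88.9% | 252/252 = 100% |
| 287 | 728 | 574 | 127% | 560/574 = 98% | 574/574 = 100% |
| 294 | 728 | 588 | 124% | 560/588 = 95.2% | 588/588 = 100% |

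The actual columns keep the SAP denominator, so only the treatment of unreturned drug differs. The reading is too high whichever column applies.

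**2. Completer, Visit 8 supply neither taken nor returned.** SAP reading 728/728 = 100%; actual (728 − 168)/728 = 560/728 = 76.9%. The rule hides 23.1 points.

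**3. Dropout who returns all unused drug, every dose taken to the last dose, ET 14 days later (assumed gap).**
- Last dose Day 35: 35/49 = 71.4%.
- Last dose Day 112: 112/126 = 88.9%.
- Last dose Day 294: 294/308 = 95.5%.

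Here the ET end date adds days without dosing and pulls the reading down.

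**4. Dosing extended 30 days for a late biopsy, all doses taken.** If Visit 9 is recorded on Day 364: (728 + 60)/728 = 108.2%. If it is recorded at the biopsy on Day 394: 788/788 = 100%.

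**5. Neither Visit 9 nor ET.** The denominator is undefined and no reading exists.

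**6. Arm-level illustration.** The documents give no non-return rate, so this is a range under assumptions: 25% dropout (Protocol 9.2.5), ET spread evenly over Days 1 to 364, all doses taken to ET, and everyone else at 100%.
- Non-returning dropouts have a median reading of 116.7%. About 31% exceed 125% and about 69% stay in the 75 to 125% band.
- Their mean is 141.6%, pulled up by very early stops (ET on Day 1 would read 56/2 = 2800%).
- With a share q of dropouts not returning drug, the arm mean is 75 + 25 × (1 + 0.416q). This gives 101.0%, 102.6%, 105.2% and 110.4% for q = 10%, 25%, 50% and 100%.

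**The case against.** The strongest reply is that the bias needs non-return. Drug is collected at Visits 3 to 9 and at ET, counts are verified, and lost capsules are documented. With no non-return rate in the documents, no aggregate effect can be shown. That stands: a reader might infer that compliance is overstated across the trial, and the documents do not support it. Patients who return their drug are untouched by this rule.

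A reader might also infer that ending the denominator at Visit 9 or ET is itself an upward bias. It is not. Because ET follows the last intake, that end date lowers the reading in dropouts who return drug (step 3). It inflates only in combination with unreturned supply. Shortening the denominator to the last dose, with nothing else changed, would worsen the Day 35 example for a patient who stopped at Day 28, from 200% to 140/56 = 250%.

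The 108% figure for extended dosing depends on how Visit 9 is dated, which the SAP leaves open. It is an ambiguity, not a demonstrated error.

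Readings above 125% would also stand out as implausible and would not pass for good compliance. That holds for many early stops. It does not hold for the completer reading 100%, nor for most non-returning dropouts under the even-spread assumption.

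Finally, the SAP bands differ from the 80% and 100% levels in Protocol 5.5.4. Those levels trigger counselling during treatment, and nothing obliges the SAP to report by them. Changing the bands is optional and not part of this point.

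**Conclusion.** The point holds, conditional on non-return, and is minor. For a patient who does not return drug, the SAP rule can only overstate compliance: by 100 points or more in the Day 35 example, by about 27 to 29 points with ET on Day 287 (126.8% against 100% or 97.6%), and by up to 23.1 points in a completer missing only the Visit 8 supply. These sizes assume no overage; extra supply that is not returned would enlarge them. Separately, the SAP leaves compliance undefined for a patient with neither Visit 9 nor ET, and leaves the end date unclear when dosing continues past a recorded Visit 9.

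A reader might infer that the per-protocol set, and through it an efficacy result, is affected. The documents do not support that. SAP 3.2.4 names no compliance threshold, and the Protocol Deviation Plan is not among the documents. Compliance is reported descriptively. Exposure is summarized separately from dosing dates (SAP 3.3.7), and trough concentrations give another view of intake in the active arms (SAP 3.5.3). No primary result changes.

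**What to change.** Amend SAP 3.3.7 as follows:

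1. Treat a dispensation that is not returned as unknown, and compute compliance over the dispensing intervals that are accounted for.
2. Show two bounds beside it, with unreturned capsules counted as all taken and as none taken. For the completer in step 2 of the working these are 76.9% and 100%. The bounds matter because dosing in unaccounted intervals may be worse than in the rest.
3. Report the number of patients with unreturned drug by arm.
4. State the end date of the denominator when dosing continues past the recorded Visit 9 date, and when both Visit 9 and ET are absent.

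The cost is a change of SAP wording and one derivation, using accountability data already collected. The downside is that some patients will have incomplete compliance data, which is an accurate description of what is known about them.

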3.4 Efficacy Assessment

All efficacy analyses will be performed using the mITT Population and repeated in for the ITT Population. Analyses of the primary and all secondary endpoints will also be repeated for PP Population. All efficacy data will be listed.

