# 6.5 Early Termination Visit and Withdrawal Procedures

The end of treatment for patients completing the study is Visit 9 (Week 52). For patients who are withdrawn from the study prior to completion, all Visit 9 procedures will be performed at an ET Visit. Liver biopsy at ET will only be performed for patients who have been on study drug for at least 6 months.

Patients who discontinue early from the study for any reason prior to completion of the treatment period will be requested to return to the clinic for an ET Visit as soon as possible after their last intake of study drug.

If a patient discontinues early from the study for any reason after completion of the treatment period but before the Safety Follow-up Visit, sites should make every attempt to bring the patient into the site for the Safety Follow-up Visit.

The following procedures will be performed at the ET Visit:

- Record concomitant medications.
- Measure body weight.
- Perform complete physical examination.
- Collect vital signs (blood pressure [3 readings], pulse rate, and body temperature) with the patient in the sitting position after 5 minutes of rest and before any blood draws.
- Collect fasting blood sample for the following:
  - o Hematology, biochemistry, coagulation, and lipid panels.
  - Lipoprotein particle size.
  - o Biomarkers (HOMA-IR, hsCRP, Pro-C3, and ELF panel).
  - o Serum pregnancy test (only for women of childbearing potential).
  - o Lipidomic analyses (in a subgroup of patients).
- Collect urine sample for urinalysis.
- Perform 12-lead ECG after the patient has been resting in the supine position for at least 10 minutes.
- Perform MRI-PDFF and cT1 imaging.
- Perform liver biopsy (if patient has been on study drug for at least 6 months) for analyses (including lipidomics in a subset of patients).
- Assess adverse events.
- Collect a PK blood sample.
- Collect returned and used/unused study drug and assess compliance.

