# 9.2.1.1 Primary efficacy analysis

The primary endpoint (ie, the percentage of patients with resolution of NASH without worsening fibrosis) will be analyzed using the ITT Population. Patients without a Week 52 (or ET, if applicable) liver biopsy will be imputed as nonresponders. The number and percentage of patients meeting the criteria for the primary endpoint will be summarized by treatment group.

The primary analysis will be conducted using the data from the 600 mg NST-4016 and placebo groups using the Cochran-Mantel-Haenszel test, stratified by biopsy fibrosis score (2 levels: F1 versus F2 or F3). The primary analysis will be based on the use of a 2-sided test at the alpha=0.05 level of significance.

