2.2.2 Sample Size Determination

A sample size of 88 patients per treatment group provides 80% power to detect a treatment effect of 22% (40% responder rate for active versus 18% placebo), assuming a dropout rate of 25%.

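### The biopsy-conditioned mITT Population is the primary population for laboratory and MRI-PDFF endpoints that need no biopsy, so their headline analyses omit collected data

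*SAP*

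**What the plan says.** SAP 3.2.3 defines mITT as "all patients from the ITT Population who have valid baseline and Week 52 (or ET, if applicable) liver biopsy measurements" and adds: "This will be the primary population for efficacy analysis". SAP 3.4 applies it throughout: "All efficacy analyses will be performed using the mITT Population and repeated in for the ITT Population". SAP 6 lists the move to mITT as a change from the protocol covering all efficacy analysis, and gives no reason for it. The same list does give a reason for demoting cT1.

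Protocol 9.2.1 had specified the ITT Population, with multiple imputation for continuous endpoints. SAP 3.1.6 and SAP 6 drop the imputation.

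The endpoints concerned are modelled as follows:
- **Liver enzymes (SAP 3.4.2.3).** Change "at each scheduled visit will be analyzed using a Mixed Model Repeated Measures (MMRM) model". Bloods are drawn at every visit.
- **hsCRP, Pro-C3, ELF and HOMA-IR (SAP 3.4.2.4 to 3.4.2.6).** A similar repeated-measures model, with sampling at Weeks 0, 16 and 52 or ET.
- **MRI-PDFF (SAP 3.4.2.7).** Separate ANCOVAs for Week 16 and for Week 52/ET.

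Protocol 6.5 schedules laboratory tests, biomarkers and MRI at the ET Visit for everyone who withdraws, but the biopsy is conditional: "Liver biopsy at ET will only be performed for patients who have been on study drug for at least 6 months".

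**The concern.** None of these endpoints depends on histology, yet a patient's data enter the headline analysis only if a valid biopsy is obtained later. The clearest case is the Week 16 MRI-PDFF model, whose sample is decided by an event about 36 weeks afterwards (52 − 16). Three kinds of data are left out:
- Week 4 to 40 enzymes and Week 16 biomarkers and MRI from patients who later withdraw without a biopsy.
- ET laboratory and MRI results from those same patients. SAP 3.1.2 would otherwise map ET visits to analysis visits by window.
- Week 52 laboratory and MRI results from completers without a valid biopsy. Protocol Appendix G lets Visit 9 be replaced by a telehealth or in-home visit, where blood can be drawn but a biopsy cannot be done.

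A repeated-measures model is chosen largely because it uses partial follow-up under a missing-at-random assumption. The biopsy condition removes many of the patients who have partial follow-up.

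The selection may also be related to outcome. Protocol Appendix E stops study drug at set ALT/AST levels, and Protocol 4.3 allows participation to end on those criteria. A patient withdrawn in this way before 6 months has no ET biopsy and is outside the headline ALT analysis because of ALT. Equal attrition across arms should not be assumed either. Interim nausea, although mild, was ordered by dose (4.3%, 9.0% and 21.3% for placebo, 300 mg and 600 mg; Protocol 1.4.1.3). That does not show differential dropout.

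**Working it through.** **Inputs.** The test is two-sided at 0.05 (Protocol 9.2.1.1: "The primary analysis will be based on the use of a 2-sided test at the alpha=0.05 level of significance"). SAP 2.2.2 gives 88 per arm, 80% power, 40% versus 18% response and 25% dropout. Allocation is 1:1:1 (Protocol 5.3).

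**1. Reproduce the plan's figure.** Two proportions, pooled variance under the null, no continuity correction, mean rate 0.29:

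n = [1.96·√(2·0.29·0.71) + 0.842·√(0.40·0.60 + 0.18·0.82)]² / 0.22² = 65.6, so 66 evaluable per arm. Power at 66 is 80.2%.

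66 / 0.75 = 88, which matches exactly. The planned dropout therefore leaves 66 evaluable of 88 per arm (198 of 264).

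**2. Assumption.** Take the 25% as the share without a valid Week 52/ET biopsy. About 22 per arm (88 − 66) are then outside mITT. This is probably on the high side for withdrawals, because those at or after 6 months are to be biopsied. On the other hand, it does not count completers without a valid biopsy.

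**3. Precision at Week 16.** If N per arm have Week 16 data in ITT and 66 in mITT, the standard-error ratio is √(N/66). Power at 66 for a difference that has 80% power at N is Φ(2.80·√(66/N) − 1.96).

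| Share of dropouts gone before Week 16 | N in ITT | SE ratio, mITT to ITT | Power at 66 for an effect with 80% at N |
|---|---|---|---|
| None | 88 | 1.155 | 68% |
| Half | 77 | 1.080 | 74% |
| All | 66 | 1.000 | 80% (no loss) |

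In the first row the reference difference is 2.80·√(2/88) = 0.42 SD. Keeping that worst-case timing but varying dropout from 15% to 30% gives power of 73% to 65%. The documents give no dropout timing, so no row can be preferred. The 80% is only a reference point, because the plan does not power these endpoints.

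**4. ALT selection.** Suppose a share f of an arm is withdrawn early for ALT and averages X U/L above the rest. Omitting them lowers that arm's observed mean by f·X. The documents supply neither value. Assuming f from 1% to 5% and X from 50 to 200 U/L, the shift is 0.5 U/L (0.01 × 50) to 10 U/L (0.05 × 200). The treatment contrast is affected only by the difference in this shift between arms. For scale, the interim placebo-adjusted ALT changes were −19 and −25.4 U/L (Protocol Table 1). This range shows sensitivity and is not an estimate.

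**The case against.** The strongest reply is that the analysis asked for is already planned. SAP 3.4 repeats every efficacy analysis in ITT, and SAP 3.1.6 uses data as available, so the ITT models already use the observed visits of patients without a biopsy. The endpoints are other secondary endpoints, whose p-values SAP 3.1.5 declares nominal. No confirmatory claim turns on the choice of population. This stands, and it limits the point to which estimate is the headline one.

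A reader might infer that patients stopped for raised ALT are removed from the ALT analysis altogether. The documents do not support that:
- Patients with at least 6 months on drug are to have an ET biopsy and stay in mITT if it is valid.
- Appendix E stops study drug, not necessarily participation, and allows restart after consultation. An early stopper could still reach a Week 52 biopsy. The 90-day validity window in SAP 3.2.3 refers to last dose/Week 52 visit and does not settle which date governs such a patient.
- ALT is also summarised in the Safety Population with shift tables (SAP 3.6, 3.6.2), and suspected drug-induced liver injury is an adverse event of special interest (SAP 2.3.6, 3.6.1).
- The interim review found no confirmed drug-induced liver injury (Protocol 1.4.1.3), although that is narrower than stopping for ALT.

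A reader might also take 15% and 68% as the expected cost. They are the worst case. Protocol 9.2.1.4 names Week 52 for the repeated-measures comparison, and there early dropouts contribute few observed values. At the interim, with 33 and 35 active patients, ALT, ALP and Pro-C3 were already at p<0.001 for both doses. Power is therefore not the main issue for ALT, but that does not answer the selection.

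**Conclusion.** The point holds for the headline analyses of the non-biopsy endpoints. SAP 3.2.3, 3.4 and 6 condition them on a later post-randomisation event, depart from the protocol's ITT rule and give no reason. The consequence is selection and some loss of precision in headline secondary estimates, not loss of type I error control.

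The precision cost at Week 16 is 0% to 15% in standard error. It rests on equating the planned 25% dropout with the lack of a valid biopsy, and on dropout timing that the documents do not give. The ALT selection is systematic only for patients withdrawn before 6 months, and otherwise depends on whether a valid biopsy is obtained. Its size cannot be derived. The change is worth making because it is cheap, but the trial's confirmatory conclusions do not depend on it.

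**What to change.** Amend three places in the SAP together, before unblinding:
- **3.2.3 and 3.4.** Limit mITT as primary population to biopsy-derived endpoints at most. Whether it should be primary for those is a separate question. For liver enzymes, hsCRP, Pro-C3, ELF, HOMA-IR and MRI-PDFF (Week 16 and Week 52/ET), make the ITT Population primary, with all available observed data in the planned MMRM or ANCOVA, and mITT supportive. No extra subset needs defining, since a patient without post-baseline values simply contributes none.
- **6.** Revise the entry on the change of population so that it agrees with 3.4, and state the reason for any use of mITT.
- **3.3.3.** Report by arm the number of patients outside mITT and the reasons, including ALT/AST stops. At present only reasons for exclusion from the PP Population are summarised.

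The cost is SAP wording and one additional summary, because both sets of analyses are already planned. The downside is that the headline population would differ between histology and non-histology endpoints, which table titles and the study report must make clear.
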